## Specific Aims

The overall objective of this application is to gather data on the feasibility and acceptability of Narrative Exposure Therapy (NET) in a pilot sample of Veterans with PTSD and history of anger and aggression. We are also interested in evaluating whether the intervention has the potential to have an effect on key clinical outcomes, including PTSD symptoms, suicidality, substance abuse, and aggression.

The following **Specific Aims** have been developed for this project:

**Aim 1:** Evaluate study feasibility and treatment delivery procedures of Narrative Exposure Therapy (NET) in Veterans with PTSD and history of anger and aggression. Data gathered will include recruitment rates, drop-out rates, adverse event frequency and severity, participant engagement in treatment, and therapist fidelity.

**Aim 2:** Collect data on appropriateness of assessment measures of key clinical constructs in the Veteran population. Clinical outcomes evaluated will include PTSD symptoms, suicidality, substance abuse, and aggression.

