In the final session, the lifeline will also be recreated. The participant will be invited to reflect on the meaning that they attribute to the events, and to develop perspectives for the future. The final session also includes asking the patient to recall a recent prosocial event where they experienced feelings of excitement, power, enjoyment, pride, or control, and to recount this in detail. Rather than continuing the story until the intensity of the emotion diminishes, however, the therapist will stop the narration at the most exciting part. This experience is intended to prime the creation of a positive associative network with prosocial experiences, and to reinforce the sense that the patient can create positive experiences in the future that are aligned with an identity consistent with their values.

To evaluate the change in PTSD symptoms over time, participants will be administered the PCL-5 and DAR at each session.

Participants randomized to TAU will be contacted by phone once each week by the study coordinator for a brief check-in and to complete a PCL-5 and DAR.

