### Evaluation of Specific Aims

**Specific Aim 1.** *Evaluate study feasibility and treatment delivery procedures of Narrative Exposure Therapy (NET) in with a history of aggression and PTSD. Data gathered will include recruitment rates, drop-out rates, adverse event frequency and severity, participant engagement in treatment, and therapist fidelity.*

To evaluate recruitment rates, we will track the number of Veterans who complete the in-person screening.. To evaluate retention rates, we will consider retention rates > 80% to be successful. Retention will be defined as completing at least 7 of 10 sessions, with the last sessions being a mutually-agreed upon final session. Retention strategies will include: 1) reminder calls, texts, and/or emails 24 hours prior to each study visit; 2) asking each participant at the end of each session about his or her intent to attend the next session; and 3) small appreciation gifts (e.g., pens, magnetized note pads, and thermoses). The second technique has been used successfully in previous clinical trials, and also provides information for assessing the assumption of ignorable attrition required for mixed effects analyses (Leon, Demirtas, & Hedeker, 2007). The third technique has proven extremely helpful in recent longitudinal studies, resulting in high retention rates (Elliott et al., 2015; Cook et al., 2015; Kimbrel, Meyer et al., manuscript in preparation; Kimbrel, Flynn et al., 2015). For those participants who drop out of treatment, we will 1) attempt to contact them to offer compensation for participation in the qualitative interview regarding their reasons for withdrawal and in the post-treatment assessments; and 2) encourage them to complete subsequent study assessments. Qualitative interviews will be audio recorded, and analyses will help identify ways that the intervention can be further tailored to reduce dropout and to meet the needs of justice-involved Veterans.

To facilitate therapist fidelity, consultation will be provided via telephone or video conferencing by national expert on NET, [name], and/or by one of the developers of the NET adaptation for traumas involving harm to others, [name]. Study therapists will evaluate treatment fidelity after every session using checklists specifically

developed for NET. This checklist will be adapted to maximize effectiveness in future trials over the course of this pilot.

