To evaluate participant retention through the 3 month assessment, we will consider the larger RCT feasible if 70% of Veterans complete the 3 month assessment. As recommended by Wisniewski and colleagues (Wisniewski, Leon, Otto, & Trivedi, 2006), we will maintain frequent participant contact throughout the evaluation period. For example, we will make intermittent phone calls to participants to check on their status, and send birthday and holiday cards to encourage a sense of community and ownership of the study.

Adverse event monitoring is discussed in detail in the Human Subjects section of this proposal. Though we do not anticipate adverse events to be frequent or severe, if we observe a problem with adverse events we will build precautions into the structure of the treatment protocol and the study design.

***Specific Aim 2. Collect data on appropriateness of assessment measures for measuring key clinical constructs in Veterans with a history of aggression. Clinical outcomes evaluated will include PTSD symptoms, suicidality, substance abuse, and aggression.***

Change scores from baseline to 3 months post-baseline on the CAPS and on measures of PTSD symptom severity, perceptions of moral injury, anger, aggression, trauma-related guilt, depression, substance use, and suicide-related constructs will be calculated using the measures listed in the baseline section above. Measures will be evaluated for acceptable variability, and for absence of floor or ceiling effects in this sample.

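### The only outcome calculation named for Aim 2 is a two-point change score, which leaves unused the PCL-5 and DAR scores collected at every session to show change over time

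*Protocol*

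**What the plan says.** Under Evaluation of Specific Aims, Specific Aim 2, the outcome calculation is "Change scores from baseline to 3 months post-baseline on the CAPS and on measures of PTSD symptom severity", together with the moral injury, anger, aggression, guilt, depression, substance use and suicide-related scales. The next sentence adds a descriptive check: "Measures will be evaluated for acceptable variability, and for absence of floor or ceiling effects in this sample". No model, test or missing-data rule is named there.

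Other sections describe data that this calculation does not use:

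- Study Visits: "To evaluate the change in PTSD symptoms over time, participants will be administered the PCL-5 and DAR at each session". Veterans randomized to TAU are telephoned weekly for a "brief check-in and to complete a PCL-5 and DAR".
- Baseline measures: the DAR is repeated at each visit to show the pattern of change during the intervention.
- Evaluation of Specific Aims, Specific Aim 1: Veterans are asked at the end of each session whether they intend to attend the next one. This is listed as a retention technique that also "provides information for assessing the assumption of ignorable attrition required for mixed effects analyses".

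No mixed-effects analysis is set out anywhere in the protocol. Data Access and Data Recipients points to a section on data analyses, but the text available contains none.

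**The concern.** The protocol states purposes that its stated calculation cannot deliver. A difference between two time points shows no course over ten sessions. It also does not exist for a Veteran whose second time point is missing, unless a value is imputed or modelled. Such a Veteran may still have several session scores on the PCL-5 and DAR, and those show how he or she was doing before contact was lost.

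The stake is the secondary interest stated under Specific Aims: "We are also interested in evaluating whether the intervention has the potential to have an effect on key clinical outcomes". If those who return are on average those who improved more, their mean change gives too favourable a picture to carry into the larger RCT that this pilot is meant to inform.

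A second, smaller problem is that the intent-to-attend answer does not appear in the schedule of measures or in the description of data acquired. If it is not written down, the purpose given for it under Specific Aim 1 cannot be met, and it cannot be reconstructed later.

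**Working it through.** **1. The protocol's own figure.** Participants: 20 enrolled at 70% eligibility gives 20 / 0.70 = 28.57, rounded up to 29 baseline assessments. This reproduces the stated 29 and is not in dispute. The protocol gives no power or precision figure for Aim 2.

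**2. Which endpoint.** Three statements need to be set side by side.

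- The Aim 2 endpoint is three months after baseline and includes the CAPS.
- The post-treatment visit is 1 to 2 weeks after the final session for completers, and 11 to 12 weeks after baseline for drop-outs and TAU. It includes the CAPS.
- The 3-month column of the schedule is a mailed packet, three months after the final session, without the CAPS.

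The CAPS change can therefore only be taken at post-treatment. The wording does not settle which visit is meant for the other scales.

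**3. How many could be missing.** The 70% criterion under Specific Aim 1 concerns the 3-month assessment, that is, the mailed packet.

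- At 70% completion: 20 × 0.70 = 14 with a change score and 6 without. The SE of a mean change rises by √(20/14) = 1.20.
- At 80% completion: 20 × 0.80 = 16 with and 4 without, √(20/16) = 1.12. The 80% is assumed here as an endpoint rate, because the protocol's own 80% concerns sessions attended.
- For the post-treatment visit no loss rate is stated.

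**4. How large a bias could be.** None of these inputs is in the protocol. A single group of 400,000 was simulated with baseline, mid-treatment and end scores averaging 0, −0.5 and −1.0 SD, so the true change is −1.0 SD. The end score goes missing more often when the observed mid-treatment change is worse (logit slope 1.5 per SD).

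| Correlation between visits | Missing | Change, endpoint only | Change, using mid-treatment score |
|---|---|---|---|
| 0.5 | 20% | −1.112 | −0.998 |
| 0.5 | 30% | −1.163 | −0.999 |
| 0.7 | 20% | −1.087 | −1.000 |
| 0.7 | 30% | −1.127 | −1.003 |
| 0.8 | 20% | −1.070 | −0.998 |
| 0.8 | 30% | −1.103 | −1.000 |

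Endpoint-only change overstates improvement by 7 to 16%. The likelihood-type estimate that uses the intermediate score recovers the truth, as it should when missingness depends only on observed scores.

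**5. Effect of assessing drop-outs.** In the 30%, correlation 0.5 row, the mean change of those missing is (−1 + 0.7 × 1.163) / 0.3 = −0.62. If a random half of them is assessed, the observed mean is (−0.7 × 1.163 − 0.15 × 0.62) / 0.85 = −1.067, so 16% becomes about 7%. The same arithmetic in the 20%, correlation 0.8 row turns 7% into about 3%.

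**6. Bias against sampling error.** The SD of change is √(2(1 − correlation)). At correlation 0.5 it is 1.0, so with 14 Veterans the SE is 1.0 / √14 = 0.267 and the bias of 0.163 is 0.61 SE. At correlation 0.8 the SD is 0.632, the SE 0.169 and the bias 0.103, again 0.61 SE.

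**The case against.** The strongest reply is that the protocol contains no rule that excludes anyone. It says that change scores will be calculated. It does not say that Veterans without an endpoint are left out or that nothing else will be done. Model choice and missing-data handling commonly sit in a statistical analysis plan, which is not at hand. A reader might infer that the plan drops every such Veteran. The documents do not say so; the absence of a value follows from the definition of a change score. This part of the objection stands. What remains is that the one calculation named does not serve the purposes stated for the session data.

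A reader might also equate leaving therapy with lacking an endpoint. The protocol does not support that. Post-treatment Follow-up Visits schedules drop-outs at 11 to 12 weeks, Specific Aim 1 offers them compensation for that assessment, and the 3-month packet goes to everyone whether or not they dropped out. Nor can 14 of 20 be attached to the CAPS or the post-treatment visit, since the 70% criterion belongs to the mailed packet.

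The purpose of Aim 2 also limits the weight of the point: "Collect data on appropriateness of assessment measures of key clinical constructs in the Veteran population". That aim is mainly descriptive, and the potential effect is a stated interest, not an estimand. The intent question is first of all a retention technique.

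Finally, the size depends on assumed selection. Nothing in the protocol shows that those who leave improve less. A harsher simulation (20 Veterans, a mean fall of 1 PCL-5 point per week over 12 weeks, 22% lost and no drop-out recovered) gives −14.4 against a true −12.2, which is 19%. It switches off the planned recovery, and its gap of 2.3 points is below one SE of about 3.1 (SD of change √((0.9 × 12)² + 2 × 36) = 13.7, divided by √20). It should not be the headline.

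**Conclusion.** The point holds as a mismatch between the data collected and the analysis named. The named change score has no value for a Veteran without the endpoint and uses none of the session-by-session PCL-5 and DAR scores, although the protocol gives showing change over time as their purpose and refers to mixed-effects analyses. A repeated-measures model on data already being collected would be a concrete and cheap improvement.

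If Veterans who improve less are missing more often, endpoint-only change overstates improvement by about 7 to 16% at 20 to 30% missing, and by about 3 to 7% if a random half of those Veterans is assessed. In these illustrations the bias is below one standard error, so it would colour the reading of the pilot but not threaten the trial. The benefit is confined to the PCL-5 and DAR. The CAPS has two time points, and a mixed model would add little for it.

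**What to change.** Under Specific Aim 2 of Evaluation of Specific Aims:

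- For the PCL-5 and DAR, estimate mean change at post-treatment and, separately, at the mailed 3-month follow-up from a mixed model using all available baseline, session or weekly, post-treatment and 3-month scores. Fit it by arm (NET, and TAU if that arm is used), since one mean over all enrolled Veterans would not describe NET. Use a simple time function suited to about 20 participants.
- Keep change scores, each with its n, for the CAPS and the other scales given two or three times. State that the CAPS endpoint is the post-treatment visit, as in the schedule of measures.
- Record the intent-to-attend answer as a data item and use it in a sensitivity analysis to assess the ignorable-attrition assumption. It is a post-baseline variable that response to treatment may affect, so simply adding it as a covariate would change what is estimated.

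The cost is slightly more analysis work and one recorded item per session. The reported mean change may be less favourable.

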### **Participant Payment**

Veterans will receive \$70 at screening baseline, \$10 at each study visit for completion of assessment measure (PCL-5), and \$80 at end-of-study follow-up. They will receive \$35 for completing and returning 3-month follow-up questionnaires. Total possible compensation for full study participation will be \$330.

For those study visits that occur in the research laboratory, participants in both arms may be provided with local bus passes in order to facilitate transportation.

### **Risk/Benefit Analyses**

With regards to completing study measures, there is a risk of discomfort or distress in answering questions, especially questions related to traumatic experiences and PTSD symptomatology. There is also a risk of discomfort or distress during narration of traumatic experiences during therapy sessions. However, distress and discomfort related to questionnaire completion are usually temporary and well-tolerated. Distress associated with narrating traumatic events is not uncommon, but it is also usually temporary and well-tolerated, and the therapy protocol requires that the distress level be diminished before the end of each therapy session. There is a potential risk associated with the loss of confidentiality of study data.

### **Protection Against Risk**

Participants are informed clearly during the initial informed consent process that the study is completely voluntary, and that they may refuse to answer any items that they do not wish to answer on the questionnaires and interviews. They are also informed that they are free to decline

participation in any procedure and can withdraw from the study at any time.

Please see “Privacy, Confidentiality, and Information Security” section for more detailed information regarding protections related to storage of electronic and hard data. To ensure confidentiality, all records will be identified by the participant’s identification number, not by name. All raw hard copy data will be kept in a locked file cabinet in a locked room. Data files will be stored in a limited access folder on a secure server to which only study staff members have access.

### **Protections Related to Undue Influence**

With regards to participant payments, careful consideration has been given to the risk of undue financial influence. Veteran participants can earn up to \$330 for full participation. We believe that the payments proposed are commensurate with the participant burden in this study. Screening, therapy visits, and follow-up procedures are lengthy, and given that the catchment area for our facility is quite large, it is not unlikely that any employed participants will need to take an entire day off in order to travel to the VA and complete the study procedures. It is necessary to provide financial incentive for them to participate because the study does not guarantee personal benefits from participation. We believe that the payments proposed are appropriate given the time and effort being asked of the participants.

### **Data Safety and Monitoring Plan**

The individuals responsible for data safety and monitoring will be [name] (PI) and the study coordinator. Mechanisms for monitoring and reporting of data safety and adverse events (AEs) will include ongoing participant contact via study personnel, to include check-ins about any adverse events, and weekly meetings between the PI and study personnel.

The PI will meet at least weekly with study personnel to discuss enrollment, participation, and any adverse events or unanticipated problems. Regular meetings between investigators, therapists and the project manager will allow for ongoing progress reports, including the number of participants currently involved in the study, attrition rates, and scheduled data collection from participants, as well as notification and review of any AEs. Safety monitoring for AEs will be conducted in real time by the PI and/or study coordinator. The following information about adverse events will be collected: 1) the onset and resolution of the AE, 2) an assessment of the severity or intensity (use existing grading scales whenever possible), 3) an assessment of the relationship of the event to the study (definitely, probably, possibly or not related), and 4) action taken (e.g., none, referral to physician, start or increase concomitant medication). The PI will determine the severity of the event, will assign attribution to the event, and will monitor the event until its resolution.

Any adverse events will be reported to the IRB in accordance with local guidelines. We will follow established laboratory procedures for reviewing events to determine if they meet criteria for reporting as an AE or SAE. In particular, we will pay close attention to any reports from participants regarding suicidal or homicidal ideation, or increases in aggression or mood dysregulation. Any such reports will be reported as required by our local Human Research Protection Program’s research reporting Standards of Practice (SOP).

Based on the study team's long-term clinical and research experience with patients with high risk psychiatric disorders such as PTSD, depression, and anxiety disorders, we have developed IRB-approved standards of practice for psychiatric emergencies. These standards have been used for several years. It is not unexpected that participants will experience increased distress associated with the assessment procedures and diagnostic clinical interviews. Our extensive clinical and research experience suggest that there is no serious risk in these patients associated with assessment and interview procedures as proposed. Over the past several years, several hundred patients with psychiatric diagnoses have participated in our research team's clinical trials at DVAMC, and there have been only rare occurrences of serious adverse events (i.e., hospitalization only) due to temporary psychiatric symptom increases. For more information regarding our standards of practice, please see section "Psychiatric Emergencies" below.

### **Psychiatric Emergencies**

The Traumatic Stress and Health Research Lab has established IRB-approved standards of practice (SOP) for the evaluation of risk of suicide and homicide. All study staff members are trained in use of the psychiatric emergencies SOP by a Ph.D. or Masters' level clinician with years of experience in working with persons with psychiatric disorders. The SOP includes a thorough risk assessment including evaluation of risk factors and protective factors associated with both suicide and homicide. Also included in the policy are differential recommendations for action based on determinations of low, moderate, or high risk. Any staff member conducting an interview in which moderate or high risk is determined will contact a senior staff person with clinical expertise in risk assessment (including the PI, co-investigator(s), and/or DVAMC's Psychiatric Emergency Clinic or the Emergency Department).

At several time points throughout the study, participants are reminded that they are asked to inform the study therapist, study coordinator, or study PI if they experience a psychiatric emergency such as homicidal or suicidal ideation. In addition, participants are provided the telephone number of study staff who they can call in the case of psychiatric emergencies, including an after-hours contact number.

### **COVID-19 Temporary Study Procedures**

Participants who are ongoing at the time of the COVID-19 crisis will complete therapy and follow-up visits via phone and/or other approved telehealth platforms. Questionnaires will be completed by mail, orally, and/or MyHealthyVet. If enrollment continues during the COVID-19 crisis, study procedures will be completed in the same manner. The consent process will take place by mail and phone.

**Safety Concerns.** Study therapists will be informed that prior to beginning therapy by telephone or telehealth platform, participants will need to identify an emergency contact for the participant to be used only in true emergencies (e.g., medical crisis, high risk suicidal ideation). Second, therapists will be asked to confirm the participant's location at the start of every appointment (the exact address is ideal) in case they need to contact local emergency personnel in the case of a psychiatric or medical emergency. If any participant expresses suicidal or homicidal ideation (SI and HI, respectively), study staff will respond using a standard of practice that has been used

successfully in our lab's past telehealth-based trials. The study staff member responsible for the call will be instructed to gather more information from the participant, including information about plan, means, intent, intended victim (in the case of HI) and history of suicidal and homicidal behavior. Any participant who expressed SI will be provided with the suicide hotline number. The participant will be informed that the PI may contact him/her to talk more about his/her SI or HI. The study coordinator will obtain current contact information for the participant and inform the PI, who will contact the participant as necessary to ensure participant safety. In cases of imminent homicidality or suicidality, which are not anticipated, we will seek guidance from the Psychiatric Emergency Clinic on best strategies for follow-up, which could include, but is not limited to, self-presentation at the VA's emergency room with the help of an emergency contact, calling 911, or calling local police for a wellness check.

